11.2.5. Efficacy Analyses

No formal hypothesis testing is planned in this Phase 1b study.

For solid tumors other than prostate cancer, tumor assessment based on investigator assessment according to RECIST v1.1 will be used to calculate ORR, DCR, PFS, and DOR, as well as timepoint estimate PFS-6m. Overall survival (OS) and OS-6m will be summarized as well. For patients with ovarian cancer, tumor response may also be assessed by investigators based on GCIG criteria which use carcinoma antigen-125 (CA-125) in combination with RECIST v1.1 ([Appendix 9](#)).

For patients with prostate cancer, PSA and tumor lesions will be evaluated together to determine the tumor response according to PCWG2 criteria ([Appendix 10](#)).

ORR is defined as the proportion of patients who have a best overall response (BOR) of CR or PR, where BOR is defined as the best response recorded from the first dose of study drugs until data cut, disease progression, or start of new anti-neoplastic treatment. Binomial exact 90% and 95% confidence intervals will be calculated for ORR in each cohort.

DCR is defined as the proportion of patients with BOR of CR, PR, and SD. It will be summarized similarly as ORR.

PFS is defined as the time from the date of the first dose of study drugs to disease progression or death, whichever occurs first.

PFS censoring rule will follow FDA *Guidance for Industry, Clinical Trial Endpoints for Approval of Cancer drugs and Biologics* (2007). Patients who have a clinical determination of progression should undergo imaging and laboratory assessments, if possible, to correlate radiographic findings with the clinical findings. Data for patients without disease progression or death by the time of analysis will be censored at the time of the last tumor assessment. Data from patients who are lost to follow-up prior to documented disease progression will be censored at the last tumor assessment date when the patient is known to be progression-free. More details will be given in the SAP.

DOR is defined as the time from the date of the earliest documented response to disease progression or death for any cause, whichever occurs earlier. Only responders will be included in the DOR calculation.

OS is defined as the time from the date of the first dose of study drugs to death.

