- No FDG-PET at baseline and a positive FDG-PET at follow-up: If the positive FDG-PET at follow-up corresponds to a new site of disease confirmed by CT, this is progressive disease. If the positive FDG-PET at follow-up is not confirmed as a new site of disease on CT, additional follow-up CT scans are needed to determine if there is truly progression occurring at that site (if so, the date of progressive disease will be the date of the initial abnormal FDG-PET scan). If the positive FDG-PET at follow-up corresponds to a pre-existing site of disease on CT that is not progressing on the basis of the anatomic images, this is not progressive disease.

Evaluation of Best Overall Response

The best overall response is the best response recorded from the start of the study until the end of the study taking into account any requirement for confirmation. On occasion a response may not be documented until after the end of therapy, so protocols should be clear if post-treatment

assessments are to be considered in determination of best overall response. Protocols must specify how any new therapy introduced before progression will affect best response. The patient’s best overall response will depend on the findings of both target and non-target disease and will also take into consideration the appearance of new lesions.

Furthermore, it also depends on the nature of the study, the protocol requirements, and result measurements. Specifically, in non-randomized studies where response is the primary endpoint, confirmation of PR or CR is needed to deem either one the “best overall response”. The best overall response is determined once all the data for the patient is known.

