4 STUDY ENDPOINTS

4.1 PRIMARY ENDPOINTS

- Escalation: Incidence and nature of DLTs
- Escalation and Expansion: Incidence, nature, and severity of AEs, graded according to the National Cancer Institute Common Terminology Criteria for Adverse Events (NCICTCAE) v.4.03 and
- Objective response rate (ORR), as assessed using RECIST v1.1

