6.3 EFFICACY ANALYSIS

6.3.1 Primary Efficacy Endpoints

Escalation:

- Dose-limiting toxicity in the DLT evaluation period will be used to determine the dose and schedule of pamiparib plus TMZ in the expansion cohorts. The DLT events will be listed for patients in the DLT Evaluable Analysis Set.

All phases:

- Incidence, nature, and severity of AEs will be summarized. Refer to Section 6.4.3 for more detail. The outputs for AEs will be summarized in SAF.
- Overall Response Rate (ORR) by investigator

Tumor status evaluation including response and progression will be assessed using RECIST v1.1 by investigator throughout this study. This criterion will be used to calculate tumor assessment endpoints including ORR, DCR, DOR and PFS.

ORR is defined as the proportion of subjects who have a best overall response (BOR) of complete response (CR) or partial response (PR), where BOR is defined as the best response recorded from the first postbaseline tumor assessment until data cutoff date, disease progression or start of new anticancer treatment. For a confirmed ORR, confirmation of CR or PR at next tumor scan (at least 4 weeks from initial documentation) is required.

Two-sided binomial exact 90% confidence intervals (CI) of ORR will also be constructed for the statistical inference of the point estimate in each cohort.

Tables for confirmed and nonconfirmed ORR will be summarized in Efficacy Evaluable Analysis Set. In addition, a listing of the tumor assessment data in SAF will also be provided. Patients without evaluable postbaseline tumor assessment will be considered as non-responders in the safety analysis set. Maximum tumor shrinkage per patient will be presented in waterfall plots.

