6.3.2 Secondary Efficacy Endpoints

- Pharmacokinetic parameters of BGB-290 and TMZ, including but not limited to C_{trough}
Refer to Section 6.3.6 for more detail.
- Disease Control Rate (DCR) by investigator

DCR is defined as the proportion of subjects with BOR of CR, PR, or stable disease (SD). Similar to ORR, two-sided binomial exact 90% confidence intervals will be calculated for DCR in each cohort. The table for DCR will be summarized in both SAF and Efficacy Evaluable Analysis Set. Patients without evaluable postbaseline tumor assessment will be considered as non-responders in the safety analysis set.

- Duration of Response (DOR) by investigator

DOR is defined as the time (month) from the date of the earliest documented CR or PR (that is subsequently confirmed) to disease progression or death due to any cause, whichever occurs earlier. The tables for confirmed and nonconfirmed DOR will be summarized in efficacy evaluable set and only responders will be included in the DOR calculation.

Kaplan-Meier method will be used to estimate DOR, and corresponding quartiles (including the median) in the responders. A two-sided 90% CIs of median will be calculated for each cohorts using generalized Brookmeyer and Crowley method (Brookmeyer & Crowley, 1982).

Censoring rule for DOR will follow PFS censoring rule mentioned in FDA Guidance for Industry Clinical Trial Endpoints for the Approval of Cancer Drugs and Biologics (2018). The censoring rules are described in Appendix 10.2.

- PFS and PFS-6m by investigator

PFS is defined as the time (months) from the date of the first dose of combination treatment to disease progression or death due to any cause, whichever occurs first. The PFS-6m is defined as the percentages of subjects who remain alive and progression-free at 6 months. PFS censoring rules are described in Appendix 10.2. If a patient meets the criteria for more than 1 censoring rule, PFS will be censored at the earliest censoring date. The tables for PFS and PFS-6m will be summarized in Efficacy Evaluable Analysis Set.

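### Confirmed and nonconfirmed ORR are both tabulated with neither named primary, and the ORR definition as worded omits the confirmation that Protocol Appendix 5 requires in this design

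*SAP*

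**What the plan says.** ORR is a primary endpoint in both documents. SAP 4.1 lists it as "Objective response rate (ORR), as assessed using RECIST v1.1", without a word on confirmation.

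The working definitions of best overall response (BOR) carry no confirmation condition either. In Protocol 11.2.5, "BOR is defined as the best response recorded from the first dose of study drugs until data cut, disease progression" or new treatment. In SAP 6.3.1, "BOR is defined as the best response recorded from the first postbaseline tumor assessment until data cutoff date", again with progression or new treatment as the other stops. The SAP then adds a separate sentence: "For a confirmed ORR, confirmation of CR or PR at next tumor scan (at least 4 weeks from initial documentation) is required". After that comes the reporting plan: "Tables for confirmed and nonconfirmed ORR will be summarized in Efficacy Evaluable Analysis Set". No order of priority is given.

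Duration of response has the same duality. SAP 6.3.2 defines it from a response that is later confirmed, and then says "The tables for confirmed and nonconfirmed DOR will be summarized in efficacy evaluable set".

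Protocol 4.1 adopts RECIST v1.1 by pointing to Appendix 5. That appendix says that "in non-randomized studies where response is the primary endpoint, confirmation of PR or CR is needed to deem either one the" best overall response. Its section on confirmatory measurement repeats the requirement for the same setting and gives measurement error as the reason.

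**The concern.** The study is open-label, describes no random allocation, has response read by the investigator, and has ORR as a primary endpoint. That is the setting for which Appendix 5 asks for confirmation. The sentences that define ORR leave confirmation out, and the SAP treats confirmed ORR as a variant rather than as the endpoint.

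Two things are at stake. First, a primary endpoint has two prespecified values and no rule for which one leads the report. In cohorts of 20-25, one or two patients separate them. Second, the sample-size text (Protocol 11.4, SAP 5) describes precision at an observed ORR of about 40% without saying which ORR is meant, so a reader cannot tell which table to hold against it.

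The two values can differ for an ordinary reason. Scans are 8 weeks apart and Protocol 7.7 lets the next scheduled scan serve as confirmation. At any data cutoff, including one for the interim report on Cohorts 1-5 that the SAP mentions, the most recent responses may not yet have a repeat.

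**Working it through.** **1. Which rule applies.**

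| Place | What it says on confirmation |
|---|---|
| Protocol 3.1, SAP 4.1 | ORR by RECIST v1.1; silent |
| Protocol 11.2.5 | BOR is the best response recorded; silent |
| SAP 6.3.1, definition | BOR is the best response recorded; silent |
| SAP 6.3.1, next sentence | Required for a confirmed ORR only |
| Protocol 7.7 | When a response counts as confirmed (repeat at least 4 weeks later); not that ORR counts only those |
| Protocol Appendix 5 | Needed for BOR in a non-randomised study with response as primary endpoint |
| SAP 8 (changes) | Radiographic basis; silent on confirmation |

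No place makes either version primary.

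**2. Reproduce the plan's figures.** SAP 6.3.1 specifies two-sided exact binomial 90% intervals. For x responders of n, the lower limit is the 5% quantile of Beta(x, n − x + 1) and the upper limit is the 95% quantile of Beta(x + 1, n − x).

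- 8/20: 21.7% to 60.6% (SAP Table 1: 22% to 61%).
- 10/25: 23.6% to 58.3% (SAP Table 1: 24% to 58%).

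The other eight rows also reproduce to rounding, the one marginal entry being 9/21 (lower limit 24.50%, printed as 24%).

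**3. Remove responses that are not confirmed.** The number lost is an assumption, shown from none to three.

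| Not confirmed | n = 20, starting at 8 | n = 25, starting at 10 |
|---|---|---|
| 0 | 8/20 = 40%, 21.7 to 60.6 | 10/25 = 40%, 23.6 to 58.3 |
| 1 | 7/20 = 35%, 17.7 to 55.8 | 9/25 = 36%, 20.2 to 54.4 |
| 2 | 6/20 = 30%, 14.0 to 50.8 | 8/25 = 32%, 17.0 to 50.4 |
| 3 | 5/20 = 25%, 10.4 to 45.6 | 7/25 = 28%, 13.9 to 46.2 |

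**4. Chance that the lower limit exceeds 20%.** This needs at least 8 of 20 or 9 of 25 responders. The chance is the binomial upper tail at the true rate.

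| True rate counted | n = 20 | n = 25 |
|---|---|---|
| 40% | 0.58 | 0.73 |
| 32% (40% × 0.8, assuming 20% not confirmed) | 0.29 | 0.41 |
| 28% (40% × 0.7, assuming 30% not confirmed) | 0.17 | 0.25 |

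**5. The confirmation rule itself.** SAP 6.3.1 asks for confirmation at the next scan; Protocol 7.7 asks for a repeat at least 4 weeks later. With scans 8 weeks apart, a sequence of PR, not evaluable, PR meets the second rule and, read literally, fails the first. Appendix 5 says that the analysis plan must address missing assessments of this kind. The SAP does not.

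**The case against.** Neither document states that unconfirmed response is the default. ORR is tied to RECIST v1.1, Appendix 5 says that BOR takes account of any confirmation requirement, Protocol 7.7 sets a confirmation interval, and the SAP defines DOR from confirmed responses. One could read confirmation as already imported. That has some force: an unconfirmed default is the natural reading of the wording, not an explicit rule. It does not settle the matter, because the SAP keeps a separate sentence for confirmed ORR and plans a nonconfirmed table without calling it supportive.

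Appendix 5 is reproduced guideline text. It also contains a branch for studies in which confirmation is not required, and ORR stands beside DLTs and adverse events as a primary endpoint. All true. Still, neither document invokes that branch, and the clause on non-randomised studies is the closest fit to this design.

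A reader might infer that the version chosen flips a go/no-go criterion at 20%. The documents do not support this. The 20% figure describes expected precision at an observed ORR near 40%. Cohorts may be closed for futility or efficacy, but no text links that to 20%. SAP Table 1 itself includes 8/22, whose exact lower limit is 19.6% (printed as 20%). Nor does every loss cross 20%: 10/25 losing one leaves 20.2%, 9/20 losing one leaves 8/20 at 21.7%, and 11/25 losing two leaves 9/25 at 20.2%. Even at a true 40%, small cohorts alone miss the bound often (step 4).

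A reader might also infer an inflated error rate or a hidden result. Protocol 11.2.5 and SAP 6 rule out formal testing, and both tables are prespecified in the same analysis set.

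**Conclusion.** The point holds as a gap in the definition of a primary endpoint. As worded, the ORR definition lacks the confirmation that the protocol's own response criteria call for in this design, and the SAP leaves two values unranked. The consequence is a free choice of headline after the data are seen, plus exposure of the nonconfirmed value to measurement error under open-label investigator reading.

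Its size cannot be fixed from the documents, which give no confirmation rate. Under the illustrative losses of one or two responses, the point estimate falls by 5 or 10 percentage points at n = 20 (40% to 35% or 30%) and by 4 or 8 points at n = 25 (40% to 36% or 32%). The lower limits move as in step 3. These cases start at the plan's 40%, close to 20% at the lower limit, and should not be read as typical. No test, power figure or sample size changes. It should be corrected, but it does not undermine the study.

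**What to change.** In SAP 6.3.1, and in Protocol 11.2.5 to match:

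- Define the primary ORR as confirmed CR or PR per Appendix 5, with a repeat assessment at least 4 weeks after first documentation as in Protocol 7.7.
- Replace the next-scan condition with a rule that says how an intervening non-evaluable scan is treated, including PR, not evaluable, PR.
- Label nonconfirmed ORR and nonconfirmed DOR (SAP 6.3.2) as supportive.
- State in SAP 5 that the 40% behind Table 1 refers to confirmed ORR.
- Reconcile the response basis for Cohort 3. Protocol 11.2.5 determines response in prostate cancer from PSA and lesions under PCWG2. SAP 6.3.1 and SAP 8 use RECIST v1.1 and radiographic response, and SAP 6.3.5 only lists PSA.

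The cost is a few sentences; both sets of tables are already planned. The headline ORR may be lower, and responses first seen shortly before a data cutoff may not yet count. The report can give the number of responses still awaiting a repeat scan at cutoff.

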6.3.2 Secondary Efficacy Endpoints

- Pharmacokinetic parameters of BGB-290 and TMZ, including but not limited to C_{trough}
Refer to Section 6.3.6 for more detail.
- Disease Control Rate (DCR) by investigator

DCR is defined as the proportion of subjects with BOR of CR, PR, or stable disease (SD). Similar to ORR, two-sided binomial exact 90% confidence intervals will be calculated for DCR in each cohort. The table for DCR will be summarized in both SAF and Efficacy Evaluable Analysis Set. Patients without evaluable postbaseline tumor assessment will be considered as non-responders in the safety analysis set.

- Duration of Response (DOR) by investigator

DOR is defined as the time (month) from the date of the earliest documented CR or PR (that is subsequently confirmed) to disease progression or death due to any cause, whichever occurs earlier. The tables for confirmed and nonconfirmed DOR will be summarized in efficacy evaluable set and only responders will be included in the DOR calculation.

Kaplan-Meier method will be used to estimate DOR, and corresponding quartiles (including the median) in the responders. A two-sided 90% CIs of median will be calculated for each cohorts using generalized Brookmeyer and Crowley method (Brookmeyer & Crowley, 1982).

Censoring rule for DOR will follow PFS censoring rule mentioned in FDA Guidance for Industry Clinical Trial Endpoints for the Approval of Cancer Drugs and Biologics (2018). The censoring rules are described in Appendix 10.2.

- PFS and PFS-6m by investigator

PFS is defined as the time (months) from the date of the first dose of combination treatment to disease progression or death due to any cause, whichever occurs first. The PFS-6m is defined as the percentages of subjects who remain alive and progression-free at 6 months. PFS censoring rules are described in Appendix 10.2. If a patient meets the criteria for more than 1 censoring rule, PFS will be censored at the earliest censoring date. The tables for PFS and PFS-6m will be summarized in Efficacy Evaluable Analysis Set.

Kaplan-Meier method will be used to estimate PFS and PFS-6m, and corresponding quartiles (including the median) in the responders. A two-sided 90% CIs of median, Q1 and Q3 will be calculated for each cohorts using generalized Brookmeyer and Crowley method (Brookmeyer & Crowley, 1982). Event free rate at the specified time point (e.g., 3, 6, 9 or 12 months) will be estimated using the Kaplan-Meier method along with the corresponding 90% CI constructed using Greenwood's formula.

- **OS and OS-6m**

OS is defined as the time (months) from the date of the first dose of combination treatment to death due to any cause. Deaths that occur on or before the data cutoff date will be considered as an event. Data from patients who are alive on or before the data cutoff date will be censored at the last known alive date. The OS-6m is defined as the percentages of subjects in the analysis population who remain alive and progression-free at 6 months. The tables for OS and OS-6m will be summarized in SAF.

Kaplan-Meier method will be used to estimate OS and OS-6m, and corresponding quartiles (including the median) in the responders. A two-sided 90% CIs of median, Q1 and Q3 will be calculated for each cohorts using generalized Brookmeyer and Crowley method (Brookmeyer & Crowley, 1982). Event free rate at the specified time point (e.g., 3, 6, 9 or 12 months) will be estimated using the Kaplan-Meier method along with the corresponding 90% CI constructed using Greenwood's formula.

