8. Female patients of childbearing potential and female partners of male study patients must agree to practice highly effective methods of birth control ([Appendix 2](#)) for the duration of the study and for ≥ 6 months after the last dose of study drug. In addition, non-sterile male patients must agree to practice highly effective methods of birth control ([Appendix 2](#)) and avoid sperm donation for the duration of the study and for ≥ 6 months after the last dose of study drug.

9. Willingness and ability to comply with all protocol-specified requirements

Dose Escalation Phase only

10. Patient must have disease that is either measurable or evaluable per RECIST v1.1 criteria.

Dose Expansion Phase only

11. Patient must have measurable disease per RECIST v1.1 criteria (except where noted below).

Note: tumor lesions used for freshly acquired biopsies should not be included as target lesions unless there are no other suitable target lesions available

12. Ovarian Cancer (Expansion Cohort 1)

- a. Patients must have received at least one line of platinum-containing therapy in the advanced or metastatic setting.
- b. Patients must not have progressed or have recurrent disease within 6 months of the completion of the last platinum-containing regimen.
 - Note: Patients can receive additional therapy after the last platinum-containing regimen as long as the criteria for platinum-sensitivity is met.
- c. Patients with known or suspected deleterious mutations in BRCA1 or BRCA2 HRD+, regardless of the molecular signature result.
 - If HRD or BRCA1/2 mutation status is unknown or has not been previously evaluated, the patient must undergo tissue screening using the Myriad myChoice® HRD diagnostic test to determine eligibility.

13. Triple-Negative Breast Cancer (Expansion Cohort 2)

- a. Patients with known or suspected deleterious mutations in *BRCA1* or *BRCA2* are classified as HRD+, regardless of the molecular signature result.
 - If HRD or BRCA 1/2 mutation status is unknown or has not been previously evaluated, the patient must undergo tissue screening using the Myriad myChoice® HRD diagnostic test to determine eligibility.
- b. 0-1 prior platinum-containing treatment in any treatment setting
 - Note: Patients could have received additional therapy after the last platinum-containing regimen as long as the other eligibility criteria are met.
- c. Received ≤ 3 prior lines of therapy in the advanced or metastatic setting

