used for lymph nodes since they usually have a definable size when normal and are frequently surrounded by fat such as in the retroperitoneum; however, if a lymph node is believed to be present and is faintly seen but too small to measure, a default value of 5 mm should be assigned in this circumstance as well). This default value is derived from the 5 mm CT slice thickness (but should not be changed with varying CT slice thickness). The measurement of these lesions is potentially non-reproducible, therefore providing this default value will prevent false responses or progressions based upon measurement error. To reiterate, however, if the radiologist is able to provide an actual measure, that should be recorded, even if it is below 5 mm.

Lesions that split or coalesce on treatment. When non-nodal lesions “fragment”, the longest diameters of the fragmented portions should be added together to calculate the target lesion sum. Similarly, as lesions coalesce, a plane between them may be maintained that would aid in obtaining maximal diameter measurements of each individual lesion. If the lesions have truly coalesced such that they are no longer separable, the vector of the longest diameter in this instance should be the maximal longest diameter for the “coalesced lesion.”

Evaluation of Non-target Lesions

While some non-target lesions may actually be measurable, they need not be measured and instead should be assessed only qualitatively at the timepoints specified in the protocol.

Complete Response (CR): Disappearance of all non-target lesions and normalization of tumor marker levels. All lymph nodes must be non-pathological in size (< 10 mm short axis).

Non-CR/Non-progressive disease: Persistence of one or more non-target lesion(s) and/or maintenance of tumor marker level above the normal limits.

Progressive Disease: Unequivocal progression (see comments below) of existing non-target lesions. (Note: The appearance of one or more new lesions is also considered progression).

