6.1 ANALYSIS POPULATIONS

- Safety Analysis Set (SAF): includes all patients enrolled into the study who receive any dose of pamiparib and/or TMZ. The Safety Analysis Set will be used for overall survival analysis and safety analyses.
- Efficacy-Evaluable Analysis Set: includes patients in the SAF who had evaluable disease in the dose escalation phase (or measurable disease in the dose expansion phase) at baseline and had at least one postbaseline tumor assessment unless discontinued treatment due to clinical progression or death prior to tumor assessment.

Evaluable disease means patients may have measurable (target lesions) or non-measurable lesions (non-target lesions); measurable disease means patients must have at least 1 measurable lesion (target lesions) and may or may not have non measurable lesions (non-target lesions).

- DLT Evaluable Analysis Set: includes patients who received $\geq 70\%$ of BGB-290 and TMZ during the DLT assessment window (Cycle 1). Additionally, patients who had a DLT event during the DLT assessment window despite receiving $< 70\%$ of the scheduled dose will also be included.
- PK Analysis Set: includes patients who received any dose of BGB-290 or TMZ, and contributed at least one plasma concentration.

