10.2 CENSORING RULES

Table 3 shows the primary censoring rules for the derivation of PFS.

Table 3 Censoring Rules for Analysis of PFS

No.	Situation	Date of Progression or Censoring	Outcome
1	No baseline tumor assessments or no post baseline tumor assessment	Reference start date (e.g., C1D1)	Censored
2	Progression documented on scheduled visit or between scheduled visits	Date of first radiologic PD assessment	Progressed
3	No progression at the time of data cutoff or withdrawal from study	Date of last adequate radiologic assessment prior to or on date of data cutoff or withdrawal from study	Censored
4	Treatment discontinuation for undocumented progression	Date of last radiological assessment of measured lesions	Censored
5	New anticancer treatment started	Date of last radiological assessment of measured lesions prior to or on date of new anticancer treatment	Censored
6	Death before first PD assessment	Date of death	Progressed
7	Death between adequate assessment visits*	Date of death	Progressed
8	Death or PD after two or more consecutive missed visit**	Date of last adequate radiologic assessment before missed tumor assessments	Censored

9	A patient meets the criteria for more than 1 censoring rules above	Date of the earliest censoring date among all events	Censored
---	--	--	----------

Abbreviations: CR=complete response, PD=progressive disease, PR=partial response, SD=stable disease.

*Adequate tumor assessment is a radiologic assessment of CR, PR, SD, non-CR/non-PD or PD as determined by investigators or by IRC.

**More than one missed visit is defined if the duration between the last tumor assessment and death or PD is longer than 2 scheduled visits, which is 17 weeks (119 days).

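### DCR counts only CR, PR and SD, so a patient without target lesions whose best result is non-CR/non-PD enters the denominator but not the numerator

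*SAP*

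**What the plan says.** **Numerator.** SAP 6.3.2: "DCR is defined as the proportion of subjects with BOR of CR, PR, or stable disease (SD". Protocol 11.2.5 agrees: "DCR is defined as the proportion of patients with BOR of CR, PR, and SD". SAP 6.3.1 bases DCR on investigator assessment by RECIST v1.1.

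**Denominators.** SAP 6.3.2: "The table for DCR will be summarized in both SAF and Efficacy Evaluable Analysis Set".

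**Who is in them.** Protocol 5.1, criterion 10, sets the escalation entry rule: "Patient must have disease that is either measurable or evaluable per RECIST v1.1 criteria". SAP 6.1 carries this into the Efficacy-Evaluable Analysis Set, which "includes patients in the SAF who had evaluable disease in the dose escalation phase (or measurable disease in the dose expansion phase) at baseline", and explains the term: "Evaluable disease means patients may have measurable (target lesions) or non-measurable lesions (non-target lesions". In expansion, Protocol 5.1 requires measurable disease apart from stated exceptions, and criterion 14f provides for mCRPC patients whose only lesions are non-measurable bone lesions.

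**Response categories.** Protocol Appendix 5 places PR and SD under target lesions and defines both on the sum of diameters. For non-target disease it gives CR, non-CR/non-progressive disease and progressive disease. The middle category is: "Persistence of one or more non-target lesion(s) and/or maintenance of tumor marker level above the normal limits". The footnote to SAP Table 3 names it separately from SD: "Adequate tumor assessment is a radiologic assessment of CR, PR, SD, non-CR/non-PD or PD as determined by investigators".

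**The concern.** For a patient with measurable disease, lack of progression without response is SD and counts as disease control. For a patient with only non-target lesions, the corresponding result has another name, and the DCR numerator does not list that name. The same clinical course is therefore scored differently according to lesion type.

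The plan also treats one patient in two ways. Non-CR/non-PD is an adequate assessment for PFS, so a patient can be progression-free for months in the PFS table and not controlled in the DCR table. At stake is the accuracy of a secondary activity measure that SAP section 6 summarises by dose level in escalation, where groups are small.

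**Working it through.** The plan gives no DCR figure to reproduce. The check traces a patient through the definitions and then sizes the effect under stated assumptions.

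**Escalation patient with only non-target lesions**
1. Eligible under Protocol 5.1, criterion 10.
2. In the Safety Analysis Set once dosed. In the Efficacy-Evaluable Analysis Set with one post-baseline assessment, because SAP 6.1 lets evaluable disease be non-target lesions.
3. No sum of target diameters exists, so neither PR nor SD can be assigned under Appendix 5.
4. Lesions persist without progression: non-CR/non-PD.
5. Not CR, PR or SD, so outside the numerator while inside both denominators.

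The overall-response table in Appendix 5 does not help, since it has no row for a patient without target lesions. Its nearest row (target lesions not completely evaluated, non-target not progressing) gives NE, which is also outside the numerator.

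**mCRPC patient with only non-measurable bone lesions.** SAP 6.1 requires measurable disease for the expansion efficacy set, so this patient is not in that set. DCR is also tabulated in the Safety Analysis Set, where steps 3 to 5 apply. The rule there that treats patients as non-responders covers only those without an evaluable post-baseline assessment, and this patient may have one.

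**Size.** Let *c* be the true disease control rate, taken as equal in both lesion types, and *f* the share with non-target-only disease, none of whom reaches CR. Then reported DCR = *c* × (1 − *f*). The documents do not give *f*; at *f* = 0 there is no effect. With *c* = 70%:
- *f* = 10%: 0.70 × 0.90 = 63%
- *f* = 20%: 0.70 × 0.80 = 56%
- *f* = 30%: 0.70 × 0.70 = 49%

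**With intervals.** SAP 6.3.2 specifies exact two-sided 90% intervals for DCR. The Clopper-Pearson method reproduces all ten rows of SAP Table 1 to the whole percent (8/20 gives 21.7% to 60.6% against 22% to 61%; 10/25 gives 23.6% to 58.3% against 24% to 58%). The table below assumes 50 escalation patients (the approximate number in SAP section 5), true control 60% in both lesion types, and *k* non-target-only patients with no CR.

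| *k* | DCR as written | 90% CI | DCR with non-CR/non-PD counted |
|---|---|---|---|
| 0 | 30/50 = 60% | 47.4% to 71.7% | 30/50 = 60% |
| 5 | 27/50 = 54% | 41.5% to 66.2% | 30/50 = 60% |
| 10 | 24/50 = 48% | 35.7% to 60.5% | 30/50 = 60% |
| 15 | 21/50 = 42% | 30.1% to 54.6% | 30/50 = 60% |

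**One dose level.** Suppose four of six patients are without progression and one of the four has only non-target lesions with non-CR/non-PD. DCR is 4/6 = 66.7% if that patient counts and 3/6 = 50.0% as written.

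**The case against.** **The text is silent; it does not prescribe failure.** No passage says these patients are failures, and a programmer might map non-CR/non-PD to SD. That is fair as a description. But no such rule is written for RECIST, and the numerator as written excludes the category. Protocol Appendix 9 Table 1 does map one non-CR/non-progressive combination to SD in patients without measurable disease, but only for those evaluable by CA-125. SAP 6.3.1 calculates DCR by RECIST, and SAP 6.3.4 only lists CA-125.

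**The Table 3 footnote is weak evidence.** It concerns PFS censoring, and its mention of an IRC looks like template wording in an investigator-assessed study. This stands. The argument does not depend on the footnote, because Appendix 5 already separates the categories.

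**Prostate response is a PCWG2 matter.** Protocol 11.2.5 sends it there, whereas SAP 6.3.1 applies RECIST to DCR throughout. The mCRPC limb rests on the SAP rule. Appendix 10 as reproduced assigns no SD category to persisting bone lesions either.

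**The effect may be small.** DCR is secondary and descriptive, no hypothesis is tested, and tumour assessments are listed by patient, so a reader could reclassify. All of this stands and limits the weight of the point. It does not make the tabulated DCR right.

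**Adding the category alone would be too generous.** Appendix 5 expects a minimum interval before SD counts, in general not less than 6 to 8 weeks. Without one, a single early assessment would count as control. This is correct, and the fix takes it in.

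**Conclusion.** The definition needs correcting. For patients without target lesions, the DCR numerator omits the category that records absence of progression, so DCR is understated in escalation (both analysis sets) and, for bone-only mCRPC patients, in the Safety Analysis Set table. The size is unknown because the number of such patients is not given. The percentages above also assume equal true control in both lesion types and no CR among the affected patients.

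Two stronger readings are not supported:
- **That DCR by dose level distorts the choice of RP2D.** Protocol 4.2.2 bases escalation on adverse events, laboratory data and PK; Protocol 11.3.2 uses DLTs to determine the expansion dose and schedule; SAP section 7 gives the recommendation to the safety review team. Protocol 4.1 does refer to all available data, but no passage names DCR as an input, and Appendix 1 Table 1 already records an RP2D.
- **That ORR is biased.** Patients without measurable disease cannot reach PR, but the protocol deliberately includes them in the escalation efficacy population, and the ORR precision argument concerns the expansion cohorts. Restricting the denominator is a presentation choice.

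**What to change.** In SAP 6.3.2:
1. Define DCR as a best overall response of CR, PR, SD or non-CR/non-PD.
2. Hold non-CR/non-PD to the same minimum interval from first dose as SD, and state that interval, because the SAP gives none for either category.
3. State the best-overall-response rule for patients without target lesions (CR, non-CR/non-PD, PD or NE), for both DCR tables.

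Record the change from Protocol 11.2.5 in SAP section 8. An escalation ORR row restricted to measurable disease is optional.

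The cost is a phrase in the definition, a short derivation rule and the matching programming. No new data are needed, since non-target response is already part of the RECIST assessment.
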